3.4 Secondary Outcomes

Smoking Rate (TLFB). We will assess the number of cigarettes smoked on each day throughout the study. A standard timeline follow-back (TLFB) method will be used [68], as we have done previously [69] to assess self-reported smoking rate.

Withdrawal Symptoms. The “Minnesota Nicotine Withdrawal Scale - Revised version”(MNWS_R) [70] captures the current state of nicotine withdrawal [71, 72]. The scale assesses eight DSM-IV items of nicotine withdrawal including: dysphoria or depressed mood, insomnia, irritability/frustration/anger, anxiety, decreased heart rate, difficulty concentrating, restlessness, and increased appetite/weight gain. Participants will rate the intensity of their symptoms on the following scale: 0 = none, 1 = slight, 2 = mild, 3 = moderate, 4 = severe and a summary score will be calculated. This will be administered at all study visits (except the Intake). Withdrawal will be assessed using a “past week” time reference for all visits except the 24-H testing visit on Day 23, which will use a 24-h time reference.

Craving. The 10-item brief QSU questionnaire on smoking urges [73] will be used to assess craving for cigarettes during the medication run-up period. The QSU-B contains 2 subscales (anticipation of reward, relief from negative affect). Craving has also been related to long-term cessation outcome in many, but not all, clinical studies [74]. This will be administered at all study visits (except the Intake). Similar to withdrawal symptoms, craving will be assessed using a “past week” time reference for all visits except the 24-H testing visit on Day 23, which will use a 24-h time reference.

Cigarette Ratings and Subjective Effects. The Cigarette Evaluation Scale (CES), developed to assess subjective effects of smoking [75], is an 11-item Likert-format measure. Questions include items for nausea and dizziness, craving relief, and

Table 1. Study Measures

State	Intake	Baseline	Remote Check-In ^b	Pre-Quit Testing	24-H Abstinent	Programmed Lapse
Study Visit Days	-1	0	7, 14	21	23 Part 1	23 Part 2
Screening Variables/Covariates						
Demographics	X					
Nicotine Dependence (FTND/Cigarette Brand)	X					
Smoking/ETOH History	X					
Medical History	X					
Height/Weight*	X	X		X		
Psychiatric/Substance Use Hx (MINI)	X					
Suicidal Ideation/Bx (C-SSRS)	X					
Bipolar Disorder Symptoms (MADRS, YMRS, additional screener) ^a	X	X	X	X	X	
Carbon Monoxide (CO)	X	X		X	X	X
Blood Pressure	X	X		X	X	
ShIPLEY Institute of Living Scale	X					
Urine Drug Screen	X	X		X	X	
Pregnancy Screen	X	X		X	X	
Depression/Anxiety (HADS)	X	X	X	X	X	
Functional Impairment (PAOFI)	X					
Risk Assessment Battery (HIV+ group only)	X					
BASIS-24	X					
SF-12	X					
Quick Inventory of Depression Symptoms	X					
Liver and Renal Function test	X					
Neuroinflammation (HIV+ group only)		X		X		
Blood Glucose		X		X	X	
Treatment Variables						
Concomitant Medication Review		X	X	X	X	
Medication Side Effects		X	X	X	X	
Pill Count			X	X	X	
Primary Outcomes						
Mood (PANAS)		X	X	X	X (24h)	X (now)
Neurocognitive Test Battery		X		X	X	
Secondary Outcomes						
Cigarette Consumption (TLFB)		X	X	X	X	X
Withdrawal (MNWS-R)		X	X	X	X (24h)	X (now)
Craving (QSU-B)		X	X	X	X (24h)	X (now)
Subjective Effects, Cigarette Ratings (CES, SQ)		X	X	X		X

*Note: Height and weight will be collected at intake visit, weight only will be collected at each subsequent study visit except day 23

^a Only administered if a diagnosis of bipolar disorder is self-reported or revealed via the MINI at intake

^b These visits will be completed remotely via phone or videoconference

enjoyment of airway sensations. The Rose Sensory Questionnaire (SQ), a 9-item Likert-format measure, will be used to assess how much they liked the cigarette smoked and how high in nicotine the cigarettes appeared to be. The questionnaire also includes a diagram of the respiratory tract and asks participants to rate the strength of the cigarette puffs on their tongue, nose, back of mouth and throat, windpipe, and chest. The CES and SQ will be administered at each visit following the Intake.

2. Statistical Analysis

Sample size and analysis. For this analysis we will be estimating summary statistics by group, including means, standard deviations, within-subject correlations, and related confidence intervals. Our sample of 18 per group will yield 95% confidence intervals with limits that fall less than 1/2 SD from the mean. For correlation, the 95% CI length will be no larger than 0.94 if $r=0$, and substantially narrower for $r \neq 0$. Because the goal of this study is to demonstrate feasibility and provide preliminary data, we will not conduct formal hypothesis testing. We will use these measures to estimate interaction effect sizes to plan future research.

3. Confidentiality

All participant information will be kept in a secure filing cabinet that is accessible only to authorized study personnel. All study databases containing participant information will be password protected, and accessible only to authorized study personnel. Any study communications made by e-mail will use ID numbers and not include names or other personal information. All data sets will use ID numbers only.

Data collected in MS Access and REDCap databases will be stored on a secure server administered by the Penn Medicine Academic Computing Services (PMACS) organization and will be restricted to only those individuals who are authorized to work on the trial. Individual user accounts with passwords will be used to restrict access to the database. Specific privilege assignments will also be employed so a user has access only to the functions necessary to complete applicable operations appropriate for their role in the trial. Additional measures to prevent unauthorized external access to the database environment will be employed using network firewall technologies. The Data Manager will maintain the database in an appropriate manner for the retention period required by regulation. Database administration includes user account maintenance, database security, performance monitoring, and database change management. Daily backups are performed to protect data against accidental destruction or corruption.

Remote study sessions will be conducted via phone or via BlueJeans, which is a HIPAA-compliant platform with security features including a room lock to ensure that communications within the platform remain private.

How will confidentiality of data be maintained? Check all that apply.

- Paper-based records will be kept in a secure location and only be accessible to personnel involved in the study.
- Computer-based files will only be made available to personnel involved in the study through the use of access privileges and passwords.
- Prior to access to any study-related information, CIRNA personnel will be required to sign statements agreeing to protect the security and confidentiality of identifiable information.
- Whenever feasible, identifiers will be removed from study-related information.
- A Certificate of Confidentiality will be obtained, because the research could place the subject at risk of criminal or civil liability or cause damage to the subject's financial standing, employability, or liability.
- A waiver of documentation of consent is being requested, because the only link between the subject and the study would be the consent document and the primary risk is a breach of confidentiality. (This is not an option for FDA-regulated research.)
- Precautions are in place to ensure the data is secure by using passwords and encryption, because the research involves web-based surveys.
- Audio and/or video recordings will be transcribed and then destroyed to eliminate audible identification of subjects.
- Other (*specify*): _____

All research personnel associated with this study have completed the CITI-Protection of Human Subjects Research Training as well as HIPAA Compliance Training. Trained staff will assess eligibility, introduce the study rationale, procedures, study risks, and collect combined informed consent/ HIPAA authorization form.

5. Privacy

The following protected health information will be collected as part of this study:

- Name
- Medical Record Number

- Street address, city, county, zip code
- Telephone numbers
- Email address
- Date of birth
- Medical and drug use history
- Social Security Number
- Results from all questionnaires, tests, or procedures
- Results from urine drug screening/pregnancy test
- Results from blood for liver/kidney function test and glucose monitoring
- Information on smoking, cognition, or HIV-related biomarkers from blood sample

Potential participants will be contacted over the phone after responding to recruitment advertisements. Participants will undergo an initial phone screening where preliminary eligibility for the research study will be determined. Only if a participant is initially eligible, will they complete Intake tasks to confirm eligibility. All data collected over the phone and during in-person visits will be collected by research staff who have completed the CITI Protection of Human Subjects Research Training as well as HIPAA Compliance Training. Information will never be recorded with identifiers other than study ID. A separate list of names with ID numbers will be accessible only by authorized personnel. All records will be kept in locked filing cabinets to maintain confidentiality. Results will not be communicated to other personnel or to the subjects. All analyses will be conducted on de-identified data. Data will be accessible to the Study Investigators, Study Physician, study staff, UPenn IRB, Office of Clinical Research, authorized UPenn staff (e.g. accounting and billing matters, provide treatment, etc.) and the Food and Drug Administration.

6. Tissue Specimens

Urine. A urine sample will be required at Intake and all testing sessions (Baseline, day 21 and day 23) for the drug and pregnancy screening. Participants who test positive for study prohibited drugs use may be deemed ineligible. Participants believed to have a false-positive result may continue in the study, with investigator approval. All female participants of child-bearing potential will complete urine pregnancy tests.

Blood. One 8.5 mL sample of blood will be drawn at the Intake visit to evaluate liver and renal function. At the Baseline and Pre-Quit Testing visits four samples (two 10 ml and two 8.5 ml) will be drawn to assess neuroinflammatory markers. A drop of blood (approximately 0.3 microliter) will also be collected at each visit following the Intake to assess blood glucose levels.

RISK/BENEFIT ASSESSMENT

1. Potential Study Risks

Potential Risks of the Medication: The following are the common side effects that have been reported with metformin XR treatment: diarrhea, nausea, and vomiting. Diarrhea led to discontinuation in 0.6% of patients. Side effects will be assessed at baseline and each subsequent visit (a total of 5 times throughout the study).

In addition to the side effects mentioned above, other rare side effects of metformin XR have been reported including: lactic acidosis, abdominal pain, constipation, distention abdomen, dyspepsia/heartburn, flatulence, dizziness, headache, upper respiratory infection, and taste disturbance.

All of these side effects shall be queried using a side effects checklist as described above.

Metformin has been shown to be safe and well-tolerated in non-diabetic individuals including normal glucose tolerant, obese African Americans [76]; obese children and adolescents [77]; individuals at risk for developing diabetes [78]; and women with polycystic ovary syndrome [79]. Nevertheless, because metformin has the potential to lower blood glucose levels, even in non-diabetic individuals, participants' blood glucose levels will be monitored at each study visit following the Intake (see Measures: Screening/Covariates for description).

For individuals currently taking anti-retroviral (HAART) medications: There are no known HAART/metformin drug interactions. Specifically, metformin is not metabolized and is excreted unchanged in the urine. The non-nucleoside reverse transcriptase inhibitors, protease inhibitors, raltegravir, and maraviroc are hepatically cleared and are therefore not contraindicated. Because dolutegravir (Tivicay) or drugs that contain dolutegravir (e.g., Triumeq) can double metformin levels, participants taking dolutegravir will be limited to no more than 1000 mg metformin per day. Therefore, individuals taking dolutegravir will be force randomized to either the placebo condition or the low dose condition.

Stringent exclusion criteria are in place to limit the chance of these side effects. Liver and kidney function will be assessed at Intake to ensure participant safety. Additionally, participants will be informed about these possible side effects and be made aware to watch for any of these symptoms and report them as soon as possible to the research staff. Participants will be instructed to take the study medication once daily with their evening meal. They will also be warned that they should limit their consumption of alcohol. All side effects will be closely monitored, and the study physician consulted should moderate or severe side effects be reported. In case any participant experiences severe side effects or an adverse event, they will be encouraged to contact the study physician ([name]) and study PI ([name]) immediately for appropriate intervention. The study physician's emergency contact numbers shall be on the medication blister pack, the study consent form, and a study brochure all participants will be provided with once they enroll into the study.

Pregnancy: There are no adequate and well-controlled studies in pregnant women with metformin. Metformin was not teratogenic in rats and rabbits at doses up to 600 mg/kg/day. This represents an exposure of about two and six times the maximum recommended human daily dose of 2000 mg based on body surface area comparisons for rats and rabbits, respectively. Determination of fetal concentrations demonstrated a partial placental barrier to metformin. Thus, metformin should not be used during pregnancy. All female participants of child bearing potential will complete a pregnancy test at the Intake session.

Blood Draw: Blood draws may result in bruising and/or slight bleeding at the needle site. This is rare and happens infrequently. Occasionally, blood drawing results in a feeling of faintness. This too is rare. A trained professional will draw blood, so the chances of these discomforts are minimal.

Inflammation Results: The blood samples collected to evaluate markers of inflammation will be stored in the PMHARC Core Lab biobank, which can be accessed only by authorized study personnel. Because this is experimental, and we do not yet understand the role of these markers in smoking behavior, participants will not receive the results or feedback from the inflammation assays.

Confidentiality and Loss of Privacy: Protection of privacy of subjects in research studies is of utmost importance, particularly when health history information is collected. Information will never be recorded with identifiers other than study ID. A separate list of names with ID numbers will be accessible only by the database manager. All records will be kept in locked filing cabinets to maintain confidentiality. Results will not be communicated to other personnel or to the subjects. All analyses will be conducted on de-identified data.

Withdrawal: Many individuals who smoke cigarettes exhibit a pattern of symptoms associated with withdrawal from cigarette use. These symptoms can include: sadness and anxiety, irritability, difficulty concentrating, anger, appetite change and weight gain, insomnia, and decreased heart rate. These events are generally of low risk. The study personnel will be trained to recognize these symptoms and educate the participants about them (e.g., their duration, methods for reducing them).

Assessments: Subjects may experience emotional distress during assessments, from discussing feelings and attitudes about smoking, or from learning about the risks from smoking. These events happen very rarely and in almost all cases are short-lived and of low intensity. Study personnel will be alerted to expect this from a small number of subjects and will be trained to make referrals for mental health services as needed. Personnel will be trained to query for adverse emotional reactions during assessments and will be trained to deal with such reactions and to provide additional referrals if needed. In addition, if assessments indicate psychiatric concerns, referrals to appropriate psychological services will be provided.

2. Potential Study Benefits

Participants who enroll in this study will benefit from the knowledge that they are contributing in an important way to potentially furthering scientific knowledge concerning ways to improve smoking cessation treatment.

3. Alternatives to Participation

At any point in the study participants may decide not to continue in their participation. As an alternative to enrolling in this study, participants may choose to continue to smoke or to seek assistance with quitting smoking through other treatment programs located in the area, other quit-smoking studies at our Center, or contacting the national quit-line.

4. Data and Safety Monitoring

Who will monitor this study? Check all that apply.

- Principal Investigator
- Sponsor or contract research organization
- NCI sponsored cooperative group
- Cancer Center (if mandated by CTSMRC)
- Medical monitor
- Safety monitoring committee
- Data and safety monitoring board

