**Application for Review of Human Research: IRB Protocol Summary
Biomedical Research**

Version 15: 8/17/2020

IRB# 824504

Names of Investigators:

Name	Department (all at UPenn)
[name]., Principal Investigator [name] [contact] [contact]	Psychiatry
[name]., Co-I	Psychiatry
[name]., Co-I	Psychiatry
[name], Study Physician	Medicine

PROTOCOL TITLE

1. Full Title

Effects of metformin on mood and cognition during nicotine withdrawal

2. Brief Title

Effects of metformin during nicotine withdrawal

STUDY SPONSORSHIP

1. Funding Sponsor

PA Department of Health

2. Primary Sponsor

University of Pennsylvania

ClinicalTrials.gov IDENTIFIER

NCT03593538

PROTOCOL ABSTRACT

There is a need for novel approaches to optimize smoking cessation treatment to help more smokers quit. Mood disturbance and cognitive deficits during nicotine withdrawal may be important treatment targets given their association with smoking relapse. In addition, factors such as HIV-1 infection may exacerbate abstinence effects on mood and cognitive deficits thus increasing the probability of smoking relapse among HIV-infected smokers (HIV+), compared to HIV-uninfected smokers (HIV-). We hypothesize that the FDA-approved medication, metformin, will attenuate withdrawal-related mood disturbance and cognitive deficits and we will explore whether HIV status moderates these effects. Using a well-validated abstinence challenge paradigm, we propose a placebo-controlled double-blind parallel arm study with one between-subjects factor of medication (low dose: 500 mg, high dose: 1500 mg, and placebo). Non-treatment seeking smokers (HIV-: n=54; and HIV+: n=30) will complete this 23-day study. After completing a baseline visit, subjects will complete 4 additional sessions (days 7, 14, 21, 23) to assess side effects, smoking rate, mood, craving, and withdrawal. Cognitive function will also be assessed on days 21 and 23. Subjects will be instructed to refrain from smoking for 24 hours prior to the laboratory session on day 23. The primary outcomes are mood and cognitive function during smoking abstinence (vs. smoking as usual). Secondary outcomes include smoking behavior (e.g., cigarettes per day, carbon monoxide) during the 3-week run-up period. These data will lay the foundation for a larger Phase IIb clinical trial.

OBJECTIVES

1. *Overall Objectives*

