 - b. Anti-psychotic medications as assessed on a case-by-case basis
 - c. Glucophage/metformin
 - d. Glyburide
 - e. Furosemide or digoxin
 - f. Nifedipine

- g. Cationic drugs (e.g., amiloride, digoxin, morphine, procainamide, quinidine, quinine, ranitidine, triamterene, trimethoprim, or vancomycin)
2. Participants who report taking prescription opiate-containing medications (Duragesic/fentanyl patches, Percocet, Oxycontin) will require physician approval prior to confirming final eligibility.
3. Current use of any smoking cessation medications (e.g., Chantix/varenicline, Zyban/bupropion, nicotine replacement therapy/gum/patch).
4. For safety reasons, HIV-infected smokers taking dolutegravir (Tivicay) or drugs that contain dolutegravir (e.g., Triumeq) should not take more than 1000 mg of metformin per day. Therefore, individuals taking dolutegravir will be forced randomized to either the placebo condition or the low dose condition.

Subjects will be instructed to refrain from using any study prohibited drugs/medications (both recreational and prescription) throughout their participation in the study. After final eligibility is confirmed, subjects who report taking contraindicated medication(s) over the course of the study period may only remain eligible if the Study Physician and/or Principal Investigator determines that the contraindicated medication(s) do/did not impact the study design, data quality, and/or subject safety/welfare. Subjects are permitted to take necessary prescription medications not included within the exclusion list during the study.

General Exclusion:

1. Current, anticipated, or pending enrollment in another research program over the next 2-3 months that could potentially affect subject safety and/or the study data/design as determined by the Principal Investigator and/or Study Physician.
2. Not planning to live in the area for the next two months.
3. Color blindness.
4. Any impairment (physical and/or neurological) including visual or other impairment preventing cognitive task performance.
5. Known allergy to study medication.
6. Planned radiologic studies involving the use of intravascular iodinated contrast materials (e.g., intravenous urogram, intravenous cholangiography, angiography, and computed tomography (CT) scans with intravascular contrast materials) during the course of study participation.
7. Inability to provide informed consent or complete any of the study tasks as determined by the Principal Investigator.

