To ensure a high level of retention and adherence in this trial we will: 1) educate subjects about the benefits of protocol compliance; 2) schedule in-person sessions at convenient times (e.g., evenings); and 3) provide modest financial compensation for session completion and transportation costs.

Referral Bonus Program

Participants who achieve their final study visit (Day 23) will be given the opportunity to receive a small bonus for referring others to the program. If the person who is referred completes the initial eligibility phone screen, regardless of outcome, the study participant will be awarded \$20 per referral, for a maximum of 3 referrals (\$60).

[figure not shown]
STUDY DESIGN

1. Phase

N/A

2. Design

We propose to conduct a randomized, placebo-controlled, parallel arm study with one between-subjects factor of medication (low dose, high dose, placebo). Once eligibility is confirmed after Intake, subjects will attend a clinic visit (day 0) to establish baseline smoking rate, mood, and cognition. Subjects will then be randomized to one of three groups (low dose: 500 mg, high dose: 1500 mg, or placebo) and will complete 4 additional sessions (days 7, 14, 21, 23) to assess side effects, smoking rate, mood, craving, and withdrawal (Figure 1). Cognitive function will also be assessed on days 21 and 23. Subjects will be instructed to refrain from smoking for 24 hours prior to the laboratory session on day 23 (Figure 1). Following FDA guidelines, the dosing regimen for metformin extended release (XR) will be 500 mg q.d for the low dose. For the high dose, the dosing regimen will be: 500 mg q.d (days 1-7); 1000 mg q.d (days 8-14); 1500 mg q.d (days 15-23).

3. Study Duration

Estimated length of time to enroll all subjects and complete the study

Enrollment will start in March 2016. We estimate that we will need to telephone screen 660 smokers to enroll 160 HIV-smokers into the study. We expect a drop-out rate of 30% based on prior experience and expect to have 54 HIV- smokers complete the study. In addition, we will telephone screen 400 HIV+ smokers to enroll 90 and have 30 HIV+ smokers complete the study. We estimate enrolling 4-5 smokers per month.

Length of a subject’s participation time in study

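### Dolutegravir may raise metformin exposure in the HIV+ low-dose arm only, so the HIV-by-low-dose effect size and the HIV+ dose contrast need an analysis in non-users

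*Combined protocol and SAP*

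**What the plan says.** Under Potential Study Risks, the protocol gives the reason for a restricted allocation: dolutegravir, alone or in a combination product, "can double metformin levels". It follows that "individuals taking dolutegravir will be force randomized to either the placebo condition or the low dose condition". The Medication part of Key Exclusion Criteria (item 4) repeats the rule and words it for HIV-infected smokers. Users therefore stay in the trial but cannot receive the high dose. No ratio between placebo and low dose is given for them.

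The Design section sets one regimen for the whole low-dose arm: it "will be 500 mg q.d for the low dose". There is no separate regimen for dolutegravir users.

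On HIV status, the abstract says "we will explore whether HIV status moderates these effects", and Overall Objectives ties the generation of effect sizes to that question. The Statistical Analysis section plans summary statistics by group without formal testing, and ends: "We will use these measures to estimate interaction effect sizes to plan future research".

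The documents describe no stratification, adjustment, subgroup or sensitivity analysis by dolutegravir use. Randomization is based on sex. Concomitant medication is recorded throughout. The HIV+ research blood samples are for inflammation markers, and no metformin level is measured. The risk section also denies any known interaction between antiretrovirals and metformin shortly before describing this one; the two statements should be reconciled.

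**The concern.** Within the low-dose arm, possible exposure is tied to HIV status. HIV- participants on 500 mg have the exposure of 500 mg. HIV+ participants on 500 mg are a mix: non-users with that exposure and users with up to twice as much. If metformin acts in an exposure-related way, an HIV-by-low-dose difference can appear with no moderation by HIV at all.

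The HIV+ comparison of 1500 with 500 mg is affected as well. Users can be in the 500 mg arm but never in the 1500 mg arm, so part of the low-dose side may have exposure nearer to the high dose. That side also contains a kind of participant who could not have been allocated to the other.

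A main-effect adjustment for dolutegravir would not deal with this, because the drug changes metformin exposure only where metformin is given.

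What is at stake is the meaning of an effect size that the pilot exists to pass on to later research.

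**Working it through.** **The plan's own precision figures.** With 18 per group, the 95% half-width for a mean is t(0.975, 17)/√18 = 0.497 SD, which agrees with the stated limit of less than half an SD. For a correlation of zero, the interval length is 2·tanh(1.96/√15) = 0.934, which agrees with 0.94. Both reproduce. Note that 18 = 54/3, the HIV- completers per arm. The HIV+ figure is 30/3 = 10 per arm if equal, with a half-width of 0.715 SD.

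**Inputs from the documents.** 54 HIV- and 30 HIV+ completers; three arms; users in placebo or low dose only; levels up to doubled.

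**Assumptions, not in the documents.** A share p of HIV+ completers takes dolutegravir; users split 1:1 over placebo and low dose; non-users split 1:1:1; no HIV- participant is a user; levels exactly double; the effect is linear at 0.3 SD per 500 mg, with unit SD.

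**Formulas.**
- HIV+ low-dose arm: n = 30[p/2 + (1−p)/3].
- User share of that arm: s = (p/2)/[p/2 + (1−p)/3] = 3p/(2+p).
- Mean exposure: 500(1+s) mg-equivalent. Gap to 1500 mg: 1500 − 500(1+s).
- Spurious HIV-by-low-dose difference: 0.3s SD.
- Half-width of the interaction, all participants: 1.96·√(2/18 + 2/n). Non-users only: 1.96·√(2/18 + 2/m), with m = 30(1−p)/3.

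| | p = 0.2 | p = 0.3 | p = 0.5 |
|---|---|---|---|
| HIV+ low-dose arm n | 11 | 11.5 | 12.5 |
| of whom users | 3 | 4.5 | 7.5 |
| user share s | 27% | 39% | 60% |
| mean exposure (mg) | 636 | 696 | 800 |
| gap to 1500 mg (1000 if no users) | 864 | 804 | 700 |
| spurious difference (SD) | 0.08 | 0.12 | 0.18 |
| half-width, all (SD) | 1.06 | 1.05 | 1.02 |
| non-users per HIV+ arm m | 8 | 7 | 5 |
| half-width, non-users (SD) | 1.18 | 1.23 | 1.40 |

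**Sensitivity.** Over p = 10% to 75%, s runs from 14% to 82%, mean exposure from 571 to 909 mg, and the spurious difference from 0.04 to 0.25 SD. At p = 0.3, slopes of 0.2 and 0.5 SD per 500 mg give 0.08 and 0.20 SD. If the HIV+ arms were instead held at 10 each, the user share at p = 0.3 would be 4.5/10 = 45% and the mean exposure 725 mg.

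**HIV+ 1500 v 500 mg at p = 0.3.** The expected contrast falls from 0.3 × 1000/500 = 0.60 SD to 0.3 × 804/500 = 0.48 SD. With all participants the half-width is 1.96·√(1/11.5 + 1/7) = 0.94 SD; in non-users it is 1.96·√(2/7) = 1.05 SD.

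**Bias against variance for the interaction.** Excluding users adds variance 2/m − 2/n = 0.068, 0.112 and 0.240 at p = 0.2, 0.3 and 0.5. The squared bias removed is 0.007, 0.014 and 0.032. Exclusion lowers mean squared error only if the slope exceeds √(added variance)/s, about 0.8 to 1.0 SD per 500 mg.

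**The case against.** The strongest objection is that the Statistical Analysis section names neither HIV nor the low-dose arm. A reader might infer that it explicitly pools dolutegravir users and non-users and promises an HIV-by-low-dose estimate. It does not. With medication as the only between-subjects factor, and abstinence compared with usual smoking, its interaction could be medication by abstinence, and its 18 per group matches the HIV- completers alone. This stands as a correction of attribution. It does not remove the point, because Overall Objectives asks for effect sizes that bear on HIV moderation.

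Three further inferences go beyond the documents:
- That low dose v placebo is balanced for dolutegravir. The protocol allows both arms but states no ratio and names only sex as a randomization factor.
- That a benefit of the higher dose is understated. This needs a response that rises with exposure, and the plan reports no human dose-response for these outcomes. With a flat response there is no bias.
- That every user has twice the level. The protocol says only that levels can double.

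It is also fair that the likely bias is small beside the sampling error, that the moderation aim is exploratory and untested, and that recorded medication use would allow the split to be made later. The bias is nevertheless systematic, and a split chosen after the results are seen is weaker than one fixed beforehand.

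Finally, making the non-user estimate the main one for the interaction would, under the assumptions above, add about 7 to 10 times the squared bias it removes. That objection succeeds and limits the remedy.

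**Conclusion.** The point holds in conditional form. The allocation rule and the protocol's own statement about metformin levels tie possible exposure to HIV status in the low-dose arm, and no planned analysis separates the two. An HIV-by-low-dose difference could therefore partly reflect exposure, and the HIV+ 1500 v 500 mg contrast could be compressed.

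The size is not knowable from the documents. It rests on the user share, their split over two arms, how far levels rise, and an assumed dose-response. It is zero if no user enters the low-dose arm or if the response is flat. In the illustrations the bias is about a ninth of the interaction's half-width at p = 0.3. This is a matter of interpretation and of what is carried into later planning. It is not an error-rate problem, since no formal test is planned. It should be corrected, but it does not undermine the study.

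**What to change.** In the Statistical Analysis section:

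1. Compute the HIV+ 1500 v 500 mg contrast among participants not taking dolutegravir. They are the only HIV+ participants who could be allocated to either dose, so this comparison is randomized and free of the exposure mix.
2. Keep the all-participants HIV-by-low-dose effect size. Beside it, report a prespecified sensitivity estimate that excludes dolutegravir users, with the number of users in each arm.
3. State that an HIV difference seen only in the all-participants estimate cannot be attributed to HIV status.

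Dolutegravir use has to be known at allocation and medication is already recorded, so no new data, visit or change to treatment is needed. The cost is some wording, one table and wide intervals in the non-user estimates: about 7 per HIV+ arm if 30% are users. The sensitivity estimate will rarely settle the question, but it shows whether the HIV finding depends on the users.
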